5.5 Description and justification of route of administration and dosage

Administration route

MSCs will be administered intranasally to prevent loss of MSC in peripheral organs and to make sure MSCs will arrive rapidly and efficiently at the injured brain region. From the nasal mucosa, MSCs cross the cribiform plate and migrate throughout the brain using the rostral migratory stream.(Danielyan et al. 2009; Danielyan et al. 2011) In an animal model of neonatal brain injury, it was demonstrated that MSCs were detected in the olfactory bulb, in the subventricular zone of the lateral ventricles and more caudally in the ischemic damaged hippocampus within 2 hours after intranasal administration.(Donega, van

Velthoven, Nijboer, van Bel, et al. 2013). We also showed improved sensorimotor outcome and decrease of gray and white matter loss after intranasal treatment with MSCs compared to vehicle treatment. It was therefore concluded that the nasal route is efficient for MSC transplantation after neonatal brain injury.(van Velthoven et al. 2010b) This finding is confirmed by a study of Wei et al, who treated rats intranasally with bone marrow-derived MSCs. At 24 days following stroke, MSCs were found to significantly reduce infarct size, promote angiogenesis, neurogenesis and neurovascular repair. Rats treated with MSCs had improved sensorimotor and social behavioral outcome compared to their placebo-treated controls.(Wei et al. 2015)

Studies of our group in the newborn baboon have shown that intranasally administered MSCs have the potential to migrate to the injured brain regions of primates(unpublished observations), in accordance with earlier shown studies in mice and rats is known that the olfactory anatomy of primates such as the baboon is more identical to human anatomy than rodent olfactory anatomy. We therefore expect the MSCs to migrate in a similar way in the newborn baby when administered intranasally.

It was hypothesized that survival of intranasally applied MSCs is better compared to intracranially applied, because MSCs are allowed to adapt to the brain environment while they migrate to the injured area. Intracranially applied MSCs are administered directly into the lesion site and therefore have no possibility to slowly adapt to the toxic ischemic milieu in the brain.(van Velthoven et al. 2010b) We expect that the risk of anti-donor response is lower when the MSCs are administered intranasally compared to intravenously, because locally administered allogeneic MSCs appear to be non- to weakly immunogenic. (Danielyan et al. 2009; van Velthoven et al. 2012). It is also hypothesized that the efficacy of intranasally applied MSCs is better compared to systemically applied MSCs because MSCs will not be attracted by other (damaged) peripheral organs, but are only allowed to migrate to the injured brain area. We have found chemotactic factors involved in regulating MSC migration to the lesion after intranasal administration, that mediate effective migration.(Donega, Nijboer, Braccioli, et al. 2014) In summary, the intranasal administration route provides an effective alternative allowing MSC treatment for brain injury without invasive methods and minimal burden for the

patient.

Administration dose

(Near)-term infants with PAIS that are included in this study will receive, 50 x 10⁶ MSCs, intranasally. Based on mean body mass, 50 x 10⁶ cells/patient is the human dose

equivalent to the dose that was effective in a mouse model of stroke $(0.5 - 1.0 \times 10^{6} \text{ cells/mouse})$.(van Velthoven et al. 2010b; van Velthoven et al. 2013; Donega, van Velthoven, Nijboer, van Bel, et al. 2013; van Velthoven et al. 2014; Donega, Nijboer, van Tilborg, et al. 2014) In another mouse study, intranasally applied human MSCs were most effective when the dosage was 2×10^{6} MSCs per mouse.(Donega, Nijboer, Braccioli, et al. 2014) In human studies with adult stroke, the dose that was administered varied between 5×10^{7} MSC/patient (Bhasin et al. 2011) to 12×10^{8} MSCs/patient (Bang et al. 2005; Honmou et al. 2011; Hess et al. 2014) However, these cells were administered intravenously or intra-arterially, probably leading to loss of cells in peripheral organs. Studies of our group in the newborn baboon (of about 1.1 kilogram) have shown that one intranasally administered dose of 30×10^{6} MSCs has the potential to migrate to the injured brain region of primates, in accordance with earlier shown studies in mice and rats.(unpublished observations)

Based on earlier evidence from our clinic, we expect to include infants with a birth weight ranging from 2.5 to 4.5 kilogram (Benders et al. 2014), and a dose of 50×10^{6} seems appropriate for this weight.

Additional products Not applicable

5.5.1 Description and justification of source and nature of MSCs

Source of MSCs

For this study, MSCs will be harvested from adult donor bone marrow. This is because MSCs can easily be obtained from bone marrow, expansion is possible and there is a high percentage (>90%) of MSC in stromal cells of the bone marrow. As described in chapter 2.1.S.1. of the IMPD, the MSCs will be harvested from healthy volunteers. The same MSCs are used in another trial in the UMC Utrecht to treat GvHD (see IMPD). The CTF of the UMC Utrecht has gained a lot of experience with MSCs from bone marrow and results from their earlier studies did not show any signs of toxicity of the cells (see chapter 1 IMPD). The MSCs from potential donors that will be used in the trial, were also tested in animal experiments (see IB). Also in other trials, MSCs are widely used. There are more than 500 ongoing studies using MSCs to treat various diseases in adults and children (http://clinicaltrials.gov).

Nature of cells

MSCs have many advantages over other types of stem cells or progenitors. First of all, they can easily be obtained from infants and adults.(Le Blanc & Mougiakakos 2012) Additionally, as described above, MSC treatment have a long therapeutic window, as they can be

administered at least until 10 days after brain injury to improve functional and behavioral outcome and lesion volume in neonatal HI mice. This is of great value, since the only available therapies for HI injury have to be given within a few hours. Besides, MSCs are hardly detectable in the brain after 3 days (Donega, van Velthoven, Nijboer, van Bel, et al. 2013), so the risk of Host-versus-Graft is very low. It is also very unlikely that MSCs will cause other adverse effects if they are no longer present in the brain after a short period of time. Our most recent study shows that no malignancies are found in the brains or in other organs of mice treated with MSCs when assessed at 14 months after start of MSC treatment at 10 days after neonatal HI.(Donega et al. 2015) Furthermore, MSCs have low immunogenicity because they do not express major histocompatibility complex (MHC) class-II antigens.(Rocha et al. 2000; Uccelli et al. 2008) This makes them excellent therapeutic candidates for allogeneic treatment.

5.6 Dosages, dosage modifications and method of administration

(Near-)Term infants with PAIS that are included in this study will receive 50 x 10⁶ MSCs in 600µL saline with 20% Human Serum Albumin (HSA) as described in section 5.5. Infants will be put in anti-Trendelenburg (of approximately 10°) position. Thirty minutes prior to delivery of the cells, the nose will be cleaned with saline using standard procedures operative at the NICU. After 30 minutes 0.6 mL MSCs will be slowly dripped into each nostril. This will be done using a sterile plastic (e.g. 1.0 mL) syringe containing the MSCs to slowly drip the MSCs directly in both nostrils.

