Animal models of neonatal brain injury provide evidence for the feasibility and efficacy of intranasal mesenchymal stromal cell (MSC) application in the treatment of PAIS. Additionally, results from human trials with MSCs in the treatment of adult stroke or other pathologic conditions provide evidence that MSC treatment is safe. This project aims at making the first step towards clinical application of MSCs to treat PAIS. Successful completion of this project will provide the first evidence of the safety and feasibility of MSCs to treat brain damage in newborn infants.

Objective: This study will assess safety and feasibility of bone marrow-derived allogeneic MSCs, administered by the nasal route, in neonates who suffered from PAIS.

Study design: A phase I/II, open-label, single-arm, single-center intervention study in the NICU at the Wilhelmina children's Hospital / University Medical Centre in Utrecht of (near-)term newborns ≥36 weeks of gestation within the first week of onset of presenting clinical symptoms.

Study population: All (near-)term newborns ≥36 weeks of gestation with or without clinical symptoms of PAIS but with a magnetic resonance imaging (MRI) confirmed PAIS (in the MCA region) will be eligible for this study. Following written parental consent, 10 patients will be included in our study.

Intervention: One dose of 50x10⁶ MSCs via the nasal route as soon as possible after confirmation of the MCA-stroke, but within the first week of onset of presenting clinical symptoms. Within 30 minutes after cleaning the nose with saline, using standard procedures operative at the NICU, the MSC will be delivered.

Main study parameters/endpoints: Our primary objective is to determine if MSC treatment in neonates with PAIS is safe in the acute setting, including vital signs at time of treatment, blood sampling before and after MSC treatment and occurrence of any adverse events.

Secondly we will investigate subacute and long-term safety of MSC treatment at 3 months, in terms of SAEs (such as infections) and cerebral tumorigenicity on MRI. Follow-up assessment at 3 months is part of regular care for neonates with PAIS.

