2.4 Study Procedures

Recruitment and inclusion

The NICU of the WKZ is known to have most expertise in neonatal stroke. Therefore, infants suspected of having PAIS will be transferred from hospitals in our region of care and also from other hospitals outside our region, to the UMCU and admitted to our NICU, allowing infants to be part of this study. Patients are eligible for our study if they meet our in- and exclusion criteria, PAIS may have been suspected with cranial ultrasound and will be confirmed within 7 days after onset of symptoms by MRI (including 3D-T1, T2 weighted, diffusion weighted imaging [DWI] and DTI sequences) and this PAIS is characterized by a predominantly unilateral ischemic lesion within the territory of the MCA, with involvement of the corticospinal tracts, cortex, white matter and basal ganglia. Following written parental consent, patients will then be included in our study. Parental consent will be obtained as soon as possible after admission at our NICU. Patients with PAIS that are diagnosed more than one week after birth are not eligible for enrolment.

Intervention period

After inclusion in our study, patients will receive MSCs as soon as possible after confirmation of the MCA-stroke, but within the first week of onset of presenting clinical symptoms. Steps to be undertaken before MSC administration include:

- A bacterial culture taken from both nostrils before administration of MSCs.
 Blood samples will be collected before administration of MSCs. Blood samples are taken routinely in the hospital for clinical purposes, but some extra material (0.5-1 mL) will be collected to determine infection markers CRP, procalcitonin and complete blood count. These samples will be combined with routine blood sampling and taken from routinely placed (arterial) catheters.
- 30 minutes prior to delivery of the MSCs, the nose will be cleaned with saline using standard procedures operative at the NICU.

After these procedures have been performed, infants will receive one dose of 50 x 10⁶ MSCs intranasally. We will use a sterile plastic (e.g. 1,0 mL) syringe containing the MSCs to slowly drip the MSCs alternatively in both nostrils.

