4. TREATMENT OF SUBJECTS

4.1 Investigational product/treatment

The treatment protocol requires that infants will receive MSCs as soon as possible after confirmation of the PAIS, but no later than the end of the first week of onset of presenting clinical symptoms. Steps to be undertaken before MSC administration include:

- A bacterial culture taken from both nostrils before administration of MSCs.
 Blood samples will be collected before administration of MSCs. Blood samples are taken routinely in the hospital for clinical purposes, but some extra material (0.5-1 mL) will be collected to determine infection markers CRP, procalcitonin and complete blood count. These samples will be combined with routine blood sampling and taken from routinely placed (arterial) catheters
- 30 minutes prior to delivery of the cells, the nose will be cleaned with saline using standard procedures operative at the NICU.

After these procedures have been performed, infants will receive one dose of 50 x 10⁶ MSCs intranasally. We will use a sterile plastic (e.g. 1,0 mL) syringe containing the MSCs to slowly drip the MSCs alternatively in both nostrils. Blood samples will be collected again at 24 hours after administration of MSCs.

The syringe with MSC will be packaged at the CT-F of the UMC Utrecht and will be delivered to the NICU by the clinical research nurse.

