From animal models of neonatal stroke we can conclude that no adverse effects have been described for MSC treatment. Our research group has also assessed long-term safety of intranasal MSC treatment. (Donega et al. 2015) At 14 months following HI no significant lesions or neoplasia were observed in the nasal tubinates, brains or other peripheral organs of mice treated intranasally with MSCs. Additionally, it has been shown that MSCs improved sensorimotor and cognitive function for at least 9 and 14 months, respectively. These results provide strong evidence of long-term safety (and efficacy) of MSC treatment following neonatal HI in mice. (Donega et al. 2015) Also a large metaanalysis on MSC treatment for various pathologies does not support tumorigenicity of MSC.(Lalu et al. 2012) Table 1 from the IB summarizes several other studies that performed administration of autologous and allogenic bone marrow derived MSCs in the treatment of several diseases. From these studies with a follow-up time of 2 months to 4 years, it was shown that (adult) patients do not have an increased risk of long-term effects, including tumorigenicity, after allogeneic MSC treatment.

Risk-benefit balance

We can conclude that MSC treatment in newborns with PAIS might be beneficial and no subacute and long-term risks are to be expected based on available evidence. Acute administration reactions, such as subacute temperature increases, are potentially to be expected, but these are expected to be transient, self-limiting and unharmful, based on the available evidence. However, this is the first study in which MSCs will be administered intranasally in humans, so potential risks might be unknown and/or unexpected. Therefore we have planned to perform a pilot (phase I/II) trial to assess safety and feasibility of MSC treatment in newborns with PAIS. Using close monitoring and (preventative) planned actions, as described in chapter 11.1e and 11.2, and tightly regulated stopping rules (see chapter 6.7) we expect to minimize or prevent risks.

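### Section 5.6 puts the whole dose in 600 µL but then calls for 0.6 mL in each nostril, which is 1.2 mL and twice what is prepared

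*Combined protocol and SAP*

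**What the plan says.** Section 5.6 gives the formulation first: infants "will receive 50 x 10⁶ MSCs in 600µL saline with 20% Human Serum Albumin (HSA"). After describing positioning and nasal cleaning, it gives the administration step: "After 30 minutes 0.6 mL MSCs will be slowly dripped into each nostril". The next sentence names the device: "This will be done using a sterile plastic (e.g. 1.0 mL) syringe containing the MSCs".

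Other sections bear on the same step:

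- **Cell dose.** The Summary gives "One dose of 50x10⁶ MSCs via the nasal route", and section 2.4 says "infants will receive one dose of 50 x 10⁶ MSCs intranasally". Sections 4.1 and 5.5 give the same number of cells.
- **Manner of giving it.** Sections 2.4 and 4.1 have staff "slowly drip the MSCs alternatively in both nostrils", with no volume per nostril.
- **Supply.** Section 4.1 speaks of one syringe: "The syringe with MSC will be packaged at the CT-F of the UMC Utrecht".
- **Cross-references.** Section 5.6 points to section 5.5, which justifies the cell dose but gives no volume. Section 5.7 places the formulation in chapter 3 of the IB, and storage and handling in the IMPD.

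**The concern.** The two volume statements stand a few sentences apart in the section that governs dosing, and they disagree by a factor of two. The word for each nostril is unambiguous, so the second statement cannot be read as a shared total without changing it. Nothing elsewhere in the protocol settles the matter: no section describes a 1.2 mL preparation, a second syringe or a volume per nostril.

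The protocol describes the trial in section 5.4 in these terms: "this is the first study in which MSCs will be administered intranasally in humans". It treats 10 infants, and its only volume instruction for the product should be one that staff can follow identically every time. Followed literally with one 600 µL syringe, the instruction uses up the product in the first nostril and leaves none for the second. That defeats the instruction itself and the alternate dripping in sections 2.4 and 4.1.

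**Working it through.** **Inputs**

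- Dose: 50 x 10⁶ cells (Summary; sections 2.4, 4.1, 5.5, 5.6).
- Prepared volume: 600 µL = 0.6 mL (section 5.6).
- Instructed volume per nostril: 0.6 mL (section 5.6).
- Nostrils: 2.
- Example syringe: 1.0 mL (sections 2.4, 4.1, 5.6).

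**Step 1. Concentration implied by the stated formulation**

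Concentration = dose / prepared volume = 50 x 10⁶ / 0.6 mL = 83.3 x 10⁶ cells/mL.

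**Step 2. Volume implied by the administration sentence**

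Total = 2 x 0.6 mL = 1.2 mL.

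- Against the preparation: 1.2 / 0.6 = 2.0 times, a shortfall of 1.2 − 0.6 = 0.6 mL.
- Against the example syringe: 1.2 − 1.0 = 0.2 mL too much.

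The stated 600 µL is therefore not reproduced from the per-nostril instruction.

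**Step 3. The possible readings**

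| Reading | Per nostril | Total | Concentration (cells/mL) | Cells per nostril | Total cells |
|---|---|---|---|---|---|
| A. 600 µL shared between nostrils | 0.3 mL | 0.6 mL | 83.3 x 10⁶ | 25 x 10⁶ | 50 x 10⁶ |
| B. 0.6 mL each, same cells in 1.2 mL | 0.6 mL | 1.2 mL | 50 x 10⁶ / 1.2 = 41.7 x 10⁶ | 25 x 10⁶ | 50 x 10⁶ |
| C. Literal, one 600 µL syringe | 0.6 mL, then 0 mL | 0.6 mL | 83.3 x 10⁶ | 50 x 10⁶, then 0 | 50 x 10⁶ |
| D. 0.6 mL each at the stated concentration | 0.6 mL | 1.2 mL | 83.3 x 10⁶ | 50 x 10⁶ | 100 x 10⁶ |

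**Step 4. Which reading fits the rest of the protocol**

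- A agrees with the stated formulation, the stated dose, the single syringe, its example size and alternate dripping. It contradicts only the per-nostril wording.
- B keeps the dose but contradicts the stated formulation and exceeds the example syringe.
- C keeps the dose but leaves one nostril untreated.
- D contradicts the stated dose. Over the expected birth weights of 2.5 to 4.5 kg (section 5.5) it would give 22 to 40 x 10⁶ cells/kg (100/4.5 to 100/2.5) instead of 11 to 20 x 10⁶ (50/4.5 to 50/2.5). Nothing in the protocol suggests that this is meant.

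Reading A is the likely intent: 0.6 mL is the 600 µL total in another unit, attached by mistake to each nostril.

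**The case against.** The strongest reply is that this is a slip of wording with little consequence. The cell dose is the same wherever it appears. The syringe arrives from the cell therapy facility already packaged, and nothing asks bedside staff to draw up or dilute anything. The sentence after the instruction speaks of both nostrils, and sections 2.4 and 4.1 have the drops alternate, so staff would probably share the 600 µL and would not empty the syringe on one side. The 1.0 mL syringe is only an example, so exceeding it is not a second error. The IB or the IMPD may already fix the fill volume.

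Most of this stands, and it limits the weight of the point. No overdose is shown, and no harm from the volume or its split can be demonstrated from the protocol. The one-sided scenario is what the literal text gives, not a prediction of what staff would do. The syringe size is corroboration only, and it favours the 0.6 mL total.

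The reply does not remove the conflict. The slip is in the operative instruction, and the conflict between 0.6 and 1.2 mL exists without the syringe comparison. If the IB or IMPD does settle the volume, section 5.6 still contradicts itself and would have to be brought into line.

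**Conclusion.** The concern holds. As written, section 5.6 prepares 0.6 mL and calls for 1.2 mL, a factor of two, so the instruction cannot be carried out with the stated preparation. The volume per nostril is left at 0.3 or 0.6 mL and, at a fixed 50 x 10⁶ cells, the concentration at 83.3 or 41.7 x 10⁶ cells/mL.

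Confidence in the textual conflict is high. That 0.6 mL in total is intended is an inference from the single syringe, the alternate dripping and the matching figure of 600 µL. The IB and IMPD were not available to confirm it. No endpoint, stopping rule or analysis depends on the volume. The sentence should be fixed because it is a wrong figure in the product's only volume instruction, not because it threatens the trial's conclusions.

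**What to change.** Check chapter 3 of the IB and the IMPD for the fill volume, then do one of the following:

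- **If 600 µL is the total (likely):** reword the sentence to give 0.6 mL in total (50 x 10⁶ MSCs), about 0.3 mL per nostril, dripped alternately.
- **If 0.6 mL per nostril is intended:** change the formulation in the first sentence of section 5.6 to 50 x 10⁶ MSCs in 1.2 mL, and name a syringe that holds it.

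The sponsor has to confirm which volume is right. The likely correction costs one sentence after a check of two existing documents; the alternative also changes the formulation and syringe text in the same section. Neither adds patients, procedures or analyses.

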5.7 Preparation and labelling of Investigational Medicinal Product

All physical, chemical and pharmaceutical properties and formulation of the MSCs are described in chapter 3 of the IB. Description of formulation of all reagents, solvents and other materials can also be found in the IB. Safety procedures during cell manufacture, biosafety qualification testing of cells, storage and handling are detailed in the Investigational Medical Product Dossier (IMPD).

Study product will be labelled in accordance with applicable laws and regulations as proposed in annex 13 of the guideline Good Manufacturing Practice

(2003/94/EG).(website http://ec.europa.eu/health/files/eudralex/vol-

4/2009_06_annex13.pdf) All labels will contain information required for regulatory as well as identification purposes.

5.8 Drug accountability

Not applicable.

6. METHODS

6.1 Study parameters/endpoints

6.1.1 Main study parameter/endpoint

Safety is defined primarily as the absence of treatment-related serious adverse events (SAEs) according to the Consolidated Standards of Reporting Trials (chapter 7.2 and bron), secondly as the absence of dose-limiting toxicity, defined as death within 24 hours after MSC transplantation or anaphylactic shock related to the MSC administration, and thirdly as the absence of adverse events at 3 months of age in terms of cerebral damage and neurodevelopmental outcome (see secondary outcome).

For acute safety, all patients will be regularly and intensively assessed, including blood sampling and vital signs, before and 24 hours after treatment, until discharge from our hospital. Also, blood sampling will be performed before and 24 hours after treatment with MSCs to determine inflammation parameters. Acute safety will be determined until discharge.

